Relationship to the trial valve will be assessed for the most current valve implanted or attempted to be implanted.

Prosthetic Valve Endocarditis

Any of the following:

- 1) Fulfillment of the following Duke criteria (56) for definite endocarditis:
 - Histologic and/or microbiologic evidence of infection at surgery or autopsy, or
 - 2 major criteria, or
 - 1 major criterion or 3 minor criteria, or
 - 5 minor criteria

Major and minor criteria are as follows:

Major Criteria:

- Blood cultures positive for Infective Endocarditis (IE)
 - Typical microorganisms consistent with IE isolated from two separate blood cultures, as noted below
 - Viridans streptococci, Streptococcus bovis, Staphylcoccus aureus, or HACEK group
 - Community-acquired enterococci in the presence of a primary focus
 - Microorganisms consistent with IE isolated from persistently positive blood cultures defined as:
 - At least two positive cultures or blood samples obtained >12 hours apart, or
 - All of three, or a majority of four or more separate cultures of blood, the first and last sample obtained > one hour apart
 - Single blood culture positive for Coxiella burnetti or an antiphase I IG antibody titer >1:800
- Evidence of endocardial involvement
 - Positive results of echocardiography for IE defined as:

^{*}Valve embolizations are not applicable to a valve that moves during the procedure but are able to be recaptured and repositioned.

Version 4.0, 15-Dec-2021

Page 116 of 131

Prosthetic Valve Endocarditis

- Oscillating intracardiac mass on a valve or supporting structures in the path of regurgitant jets or on implanted material in the absence of an anatomic explantation, or
- Abscess, or
- New partial dehiscence of a valvular prosthesis
- New valvular regurgitation (worsening or changing or pre-existing murmur not sufficient)

Minor Criteria:

- Predisposition: predisposing heart condition or intravenous drug use
- Fever: temperature >38°C
- Vascular phenomena: major arterial emboli, septic pulmonary infarcts, mycotic aneurysm, intracranial hemorrhage, conjunctival hemorrhages, and Janeway's lesions
- Immunological phenomena: glomerulonephritis, Osler's nodes, Roth's spots, and rheumatoid factor
- Microbiological evidence: positive blood culture but does not meet a major criterion (as noted above) or serological evidence of active infection with organism consistent with infectious endocarditis.
- Echocardiographic findings: consistent with IE but do not meet a major criterion as noted above

If only 1 major and 1-2 minor criteria are fulfilled, or if only 3-4 minor criteria are fulfilled, the event will be coded as "possible endocarditis"

- 2) Evidence of abscess, paravalvular leak, pus, or vegetation confirmed as secondary to infection by histological or bacteriological studies during a re-operation
- 3) Findings of abscess, pus, or vegetation involving the trial device at autopsy

Prosthetic Valve Dysfunction	
Stenosis: mild	For subjects with BSA \geq 1.6 m ² : Mean aortic gradient \geq 20 and \leq 40 mmHg, EOA \geq 0.8 and \leq 1.1 cm ² AND/OR DVI \geq 0.25 and \leq 0.35
	For subjects with BSA < 1.6 m ² : Mean aortic gradient \ge 20 and \le 40 mmHg, EOA \ge 0.6 cm ² and \le 0.9 cm ² AND/OR DVI \ge 0.25 and \le 0.35
Stenosis: moderate/severe	For subjects with BSA ≥ 1.6 m ² : Mean aortic gradient > 40 mmHg, EOA < 0.8 cm ² AND/OR DVI < 0.25 For subjects with BSA < 1.6 m ² : Mean aortic gradient > 40 mmHg, EOA < 0.6 cm ² AND/OR DVI < 0.25

Version 4.0, 15-Dec-2021

Page 117 of 131

Prosthetic Valve Dysfunction	
Paravalvular regurgitation: moderate	Moderate paravalvular regurgitation (per echo criteria in CIP)
Paravalvular regurgitation: severe	Severe paravalvular regurgitation (per echo criteria in CIP)
Transvalvular regurgitation: moderate	Moderate transvalvular regurgitation (per echo criteria in CIP)
Transvalvular regurgitation: severe	Severe transvalvular regurgitation (per echo criteria in CIP)

Notes:

- DVI = Doppler Velocity Index (LVOT VTI/valve VTI)
- For subjects LVOT diameter > 2.5 cm, the DVI criteria for significant (moderate or severe) stenosis is 0.2
- Reporting of prosthetic valve dysfunction will be based on core lab values (if available).
- Prosthetic valve dysfunction events are not reported as adverse events, unless the dysfunction is
 accompanied with clinical sequelae at the time of event detection, and the clinical sequelae are
 chronologically and physiologically associated with the dysfunction. However, prosthetic dysfunctions
 that are associated with adverse events, and that meet the definition of a serious adverse event, should
 be reported as such.

Device Success at 30 days

All the following

- Freedom from mortality AND
- Correct positioning of a single prosthetic heart valve into the proper anatomical location AND
- Intended performance of the prosthetic heart valve (no prosthesis-patient mismatch and mean aortic valve gradient <20 mmHg or peak velocity <3 m/s) AND
- No moderate or severe prosthetic valve regurgitation)

Prosthesis-Patient Mismatch (PPM)⁶⁴

For subjects with BMI < 30 kg/m²

- Moderate PPM: EOAI = 0.85 0.65 cm²/m²
- Severe PPM: EOAI = $\leq 0.65 \text{ cm}^2/\text{m}^2$

For subjects with BMI \geq 30 kg/m²

- Moderate PPM: EOAI = $0.70 0.55 \text{ cm}^2/\text{m}^2$
- Severe PPM: EOAI = $\leq 0.55 \text{ cm}^2/\text{m}^2$

Version 4.0, 15-Dec-2021

Page 118 of 131

Bioprosthetic Valve Dysfunction

Any of the following

- Hemodynamic structural valve dysfunction (HSVD): Mean gradient ≥ 20mmHg
- Non-structural valve dysfunction (NSVD): severe PPM or ≥ moderate aortic regurgitation
- Thrombosis
- Endocarditis
- Aortic valve reintervention

Early Safety (at 30 days)65

A composite of

- All-cause mortality
- All stroke (disabling and non-disabling)
- Life-threatening bleeding
- Acute kidney injury—Stage 2 or 3 (including renal replacement therapy)
- Coronary artery obstruction requiring intervention
- Major vascular complication
- Valve-related dysfunction requiring repeat procedure (BAV, TAVI, or SAVR)

Clinical Efficacy (after 30 days)

A composite of

- All-cause mortality
- All stroke (disabling and non-disabling)
- Requiring hospitalizations for valve-related symptoms or worsening congestive heart failure
- NYHA class III or IV
- Valve-related dysfunction (mean aortic valve gradient ≥20 mmHg, EOA ≤0.9-1.1 cm² and/or DVI<0.35m/s, AND/OR moderate or severe prosthetic valve regurgitation)

^{*}HSVD and NVSD are based on Echo core lab data, and events thrombosis, endocarditis and aortic valve reintervention are from CEC adjudications.

Version 4.0, 15-Dec-2021

Page 119 of 131

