10.1.2 Baseline

The following assessments must be completed within 14 days prior to TAVR index:

- Clinical assessment including physical examination
- Laboratory tests glomerular filtration rate (GFR), hemoglobin, international normalized ratio (INR) for subjects on warfarin, and serum creatinine
- Use of relevant medications including anticoagulants and antiplatelets
- NYHA classification
- Modified Rankin Score (mRS)
- 6 Minute Walk Test (refer to Appendix Section 18.1)
- Quality of Life Questionnaires: EQ-5D and KCCQ
- Adverse Event Review

Version 4.0, 15-Dec-2021

Page 35 of 131

• Syntax score and TTE, to confirm eligibility criteria, if not determined at the Screening Visit (per Section 10.1.1) or prior to submission for Confirmation of Qualification

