10.1.5 Follow-Up Evaluations

All treated subjects will undergo follow-up evaluations at the following time points post procedure. See section 10.3 for appropriate visit windows.

30 days (between 30 – 45 days post procedure)

- Clinical Assessment including physical examination
- Use of relevant medications including anticoagulants and antiplatelets
- NYHA Classification
- TTE
- 6-minute Walk Test (refer to Appendix Section 18.1)
- Quality of Life Questionnaires- EQ-5D and KCCQ
- 12-Lead ECG
- Adverse Event Review

12 Months (Day 365 + 30 days)

- Clinical Assessment including physical examination
- Use of relevant medications including anticoagulants and antiplatelets
- NYHA Classification
- TTE
- 6-minute Walk Test (refer to Appendix Section 18.1)
- Quality of Life Questionnaires- EQ-5D and KCCQ
- 12-Lead ECG
- Adverse Event Review
- Stress echocardiogram- (conducted at select sites. A CIP addendum detailing the assessment will be provided separately)

2 Years (Implant anniversary date and ± 30 days)

- Clinical Assessment including physical examination
- Use of relevant medications including anticoagulants and antiplatelets
- NYHA Classification
- TTE
- 6-Minute Walk test (refer to Appendix Section 18.1)
- Quality of Life Questionnaires- EQ-5D and KCCQ
- Adverse Event Review

Annual 3-5 years (Implant anniversary date and ± 60 days)

- Clinical Assessment including physical examination
- Use of relevant medications including anticoagulants and antiplatelets

SMART Trial Clinical Investigation Plan	Form
Version 4.0, 15-Dec-2021 Page 38 of 131	Medtronic

- NYHA Classification
- TTE
- 6-Minute Walk test (refer to Appendix Section 18.1)
- Quality of Life Questionnaires- EQ-5D and KCCQ
- Adverse Event Review

Other Evaluations

- In addition to an assessment at baseline, a Modified Rankin Score assessment should be conducted at 30 and 90 days after onset of any confirmed or suspected neurological event.
- In addition to laboratory tests at baseline, laboratory test results relevant for event adjudication (i.e., hemoglobin to adjudicate bleeding events) should be collected

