	Sustained (>30 min) episode of hypoperfusion evidenced by systolic blood pressure <90 mm Hg and/or, if available, cardiac index <2.2 L/min per square meter determined to be secondary to cardiac dysfunction and/or the requirement for parenteral inotropic or vasopressor agents or mechanical support (e.g., IABP, extracorporeal circulation, VADs) to maintain blood pressure and cardiac index above those specified levels.
	Note: Transient episodes of hypotension reversed with IV fluid or atropine do not constitute cardiogenic shock. The hemodynamic compromise (with or without extraordinary supportive therapy) must persist for at least 30 min.
Other cardiovascular	Hospitalization for any other cardiovascular-related reason that does not fit into one of the other categories. Examples of "other cardiovascular" hospitalizations include suspicion or diagnosis of
	endocarditis, suspicion or diagnosis or prosthetic valve thrombosis, prosthetic valve leaflet thickening or immobility, bleeding event related to anti-thrombotic therapy, suspected or confirmed bioprosthetic valve dysfunction, new peripheral vascular or aortic disorders, etc.

Non-Cardiovascular Hospitalizations

Includes hospitalizations not due to cardiovascular causes as mentioned above.

Bleeding Complications	
Life-threatening or disabling bleeding	 Fatal bleeding (BARC type 5) OR Bleeding in a critical organ, such as intracranial, intraspinal, intraocular, or pericardial necessitating pericardiocentesis, or intramuscular with compartment syndrome (BARC type 3b and 3c) OR Bleeding causing hypovolemic shock or severe hypotension requiring vasopressors or surgery (BARC type 3b) OR Overt source of bleeding with drop in hemoglobin ≥5 g/dL or whole blood or packed red blood cells (RBCs) transfusion ≥4 units* (BARC type 3b)
Major bleeding (BARC type 3a)	 Overt bleeding either associated with a drop in the hemoglobin level of at least 3.0 g/dL or requiring transfusion of 2 or 3 units of whole blood/RBC, or causing hospitalization or permanent injury, or requiring surgery AND Does not meet criteria of life-threatening or disabling bleeding
Minor bleeding (BARC type 2 or 3a, depending	Any bleeding worthy of clinical mention (e.g. access site hematoma) that does not qualify as life-threatening, disabling, or major

Version 4.0, 15-Dec-2021

Page 111 of 131

Bleeding Complications	
on the severity)	

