*Given one unit of packed RBC typically will raise hemoglobin concentration by 1 g/dL, an estimated decrease in hemoglobin will be calculated; BARC: Bleeding Academic Research Consortium; RBC: red blood cell

Notes

- 1. With respect to blood transfusions, it is critical to acknowledge that a bleeding complication has to be the result of overt bleeding and cannot be adjudicated based on blood transfusions alone.
- 2. Pre-operative hemoglobin will be used to determine severity of bleeding events
- 3. Minor bleeding (VARC-2) can be categorized to VARC-3 Type 1; Major bleeding (VARC-2) can be categorized to VARC-3 Type 2; Life-threatening or disabling bleeding (VARC-2) can be categorized to VARC-3 Type 3 and Type 4.

Acute Kidney Injur	Acute Kidney Injury (up to 7 days post procedure)	
Stage 1	 Increase in serum creatinine to 150%-199% (1.5-1.99 x increase compared with baseline) OR increase of ≥0.3 mg/dL (≥26.4 mmol/L) OR Urine output <0.5 mL/kg/h for >6 but <12 h 	
Stage 2	 Increase in serum creatinine to 200%-299% (2.0%-2.99% increase compared with baseline) OR Urine output <0.5 mL/kg/h for >12 but <24 h 	
Stage 3*	 Increase in serum creatinine to ≥300% (>3 x increase compared with baseline) OR serum creatinine of ≥4.0 mg/dL (≥354 mmol/L) with an acute increase of at least 0.5 mg/dL (44 mmol/L) OR Urine output <0.3 ml/kg/h for ≥24 h OR Anuria for ≥12 h 	

Note: *Patients receiving renal replacement therapy are considered to meet Stage 3 criteria irrespective of other criteria.

Vascular Access Site and Access Related Complications	
Major vascular complication	 Any aortic dissection, aortic rupture, annulus rupture, left ventricle perforation, or new apical aneurysm/pseudoaneurysm OR Access site or access-related vascular injury (dissection, stenosis, perforation, rupture, arterio-venous fistula, pseudoaneurysm, hematoma, irreversible nerve injury, compartment syndrome, percutaneous closure device failure) leading to death, life-threatening or major bleeding, visceral ischemia, or neurological impairment OR Distal embolization (noncerebral) from a vascular source requiring surgery or resulting in amputation or irreversible end-organ damage OR The use of unplanned endovascular or surgical intervention associated with death, major bleeding, visceral ischemia or neurological impairment OR

Version 4.0, 15-Dec-2021

Page 112 of 131

Vascular Access Site and Access Related Complications	

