7.10 Safety Evaluation

CEC adjudicated adverse events will be summarized at 30 days, 1 year, and annually through 5 years. The number of events, number of subjects with event, and the Kaplan-Meier event rate (cumulative incidence) will be reported for each category and time point by treatment arm.

Additionally, a summary of procedure related adverse events, and device related adverse events will be reported by MedDRA system organ class and preferred term by treatment arm. Device deficiencies including deficiencies which could have led to a serious adverse device effect and listing of subject deaths will also be reported.

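### The bleeding-severity note fixes pre-operative haemoglobin as the reference with no time limit, so a later bleed graded only on its haemoglobin drop may be over- or under-graded

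*Protocol*

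**What the plan says.** The bleeding definitions are in Protocol 18.5.1 (Appendix V). Two grades have a haemoglobin route. One of the life-threatening criteria is "Overt source of bleeding with drop in hemoglobin ≥5 g/dL or whole blood or packed red blood cells (RBCs) transfusion ≥4 units". The major category begins "Overt bleeding either associated with a drop in the hemoglobin level of at least 3.0 g/dL or requiring transfusion of 2 or 3 units" and continues with further alternatives, "or causing hospitalization or permanent injury, or requiring surgery". Anything less is minor. Note 2 under the table then sets the reference value: "Pre-operative hemoglobin will be used to determine severity of bleeding events". It is not restricted to procedural bleeding or to any period.

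The only scheduled haemoglobin is at baseline, within 14 days before TAVR. Protocol 10.1.2 lists "Laboratory tests glomerular filtration rate (GFR), hemoglobin, international normalized ratio (INR) for subjects on warfarin, and serum creatinine", and Table 4 shows laboratory tests at that visit only. For later events, Protocol 10.1.5 adds that "laboratory test results relevant for event adjudication (i.e., hemoglobin to adjudicate bleeding events) should be collected", without saying which value serves as the reference.

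Protocol 12.1 collects the Appendix V events for the whole trial, and Protocol Section 6 has endpoint-related events adjudicated. SAP 7.10 states: "CEC adjudicated adverse events will be summarized at 30 days, 1 year, and annually through 5 years". It reports numbers of events, numbers of subjects and Kaplan-Meier rates by arm.

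**The concern.** A drop in haemoglobin grades a bleed sensibly only if it is the drop that belongs to that bleed. The pre-operative value is a good reference for bleeding at or soon after the procedure. Months or years later, haemoglobin may have moved for other reasons: loss at the procedure that never fully recovered, correction of anaemia that was present before TAVR, or chronic illness. Read as written, Note 2 puts that movement into the drop.

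Other definitions in the same appendix do limit time or choose a reference suited to the event. Acute kidney injury stops at 7 days, disabling stroke is judged against the patient's state before that stroke, and sub-clinical valve thrombosis is judged against the discharge gradient. The bleeding note has no such limit.

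At stake are the severity grades of late bleeds in the long-term comparison of two devices.

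**Working it through.** There is no stated figure to reproduce. The check sets the rule beside its criteria and works through the arithmetic. The documents give no haemoglobin values after TAVR, so every value below is an assumption, with no transfusion.

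**1. Size of the error.** Let s = pre-operative haemoglobin − haemoglobin just before the bleed. Then

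drop under Note 2 = pre-operative − lowest value = (pre-bleed − lowest value) + s = true drop + s.

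With s = 0 nothing changes.

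**2. Illustrations (g/dL).**

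| Case | Pre-op | Before bleed | Lowest | s | True drop | Drop under Note 2 | Grade on the haemoglobin criterion: true → Note 2 |
|---|---|---|---|---|---|---|---|
| A | 13.0 | 11.0 | 9.5 | +2.0 | 1.5 | 3.5 | below major → major |
| B | 10.5 | 12.5 | 9.0 | −2.0 | 3.5 | 1.5 | major → below major |
| C | 13.0 | 11.0 | 7.5 | +2.0 | 3.5 | 5.5 | major → life-threatening |
| D | 10.0 | 13.5 | 8.0 | −3.5 | 5.5 | 2.0 | life-threatening → below major |
| E | 13.0 | 10.0 | 9.8 | +3.0 | 0.2 | 3.2 | below major → major |

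Case E is a second bleed. Suppose the first was procedural and reached 9.5, so 13.0 − 9.5 = 3.5, correctly major. The second inherits that loss, and because SAP 7.10 counts events as well as subjects, the event count can rise.

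**3. Which true drops change grade.**
- s positive: true drops from 3.0 − s up to 3.0, and from 5 − s up to 5, move up. For s = 1 these are 2–3 and 4–5; for s = 2 they are 1–3 and 3–5.
- s negative: true drops from 3.0 up to 3.0 + |s|, and from 5 up to 5 + |s|, move down. For |s| = 1 these are 3–4 and 5–6; for |s| = 2 they are 3–5 and 5–7.

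**4. Which bleeds are exposed.**
- Fatal bleeding, critical-organ bleeding, shock or severe hypotension, and transfusion of at least 4 units are life-threatening whatever the haemoglobin. They do not depend on the reference.
- Transfusion of 2 or 3 units, hospitalization, permanent injury and surgery make a bleed at least major without a drop. For these only the step at ≥5 g/dL depends on the reference. Case D, if hospitalized, stays major instead of life-threatening.
- All other overt bleeds depend on the reference at both thresholds.

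**5. Where the grade is used.** Bleeding is in neither primary endpoint and in no powered secondary endpoint. The one named endpoint with a bleeding component is the early safety composite, limited to 30 days and descriptive (SAP 7.9.4). Life-threatening bleeding enters it directly. Major bleeding enters only through a major vascular complication. A bleed like case C between discharge and day 30 would enter under Note 2 alone, but nothing in the documents shows whether such events occur. Beyond that, the grade feeds the SAP 7.10 tables.

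**The case against.** The strongest reply is that haemoglobin is one route among many. Hospitalization alone makes a bleed major, and the protocol needs only 24 hours or a change of calendar date for that, so many serious late bleeds reach at least major regardless. A reader might infer that every bleeding event, or every late one, is misgraded. The documents do not support that: the reference matters only where the haemoglobin criterion decides the grade, and only if haemoglobin has shifted.

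A second reply is that adjudicators need not apply the note mechanically. The major definition asks for a drop associated with the bleed, sites are asked for relevant haemoglobin results, and physicians adjudicate under a charter that is not among the documents. This is fair, and the charter may already handle late bleeds. But the written rule names one reference and no other, so a charter that used another value would contradict the protocol.

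Third, bleeding is not named in SAP 7.10, and the minimum adjudication scope in Protocol 13.1 is narrower than in Section 6. Long-term reporting of bleeding grades is therefore inferred from its place in Appendix V. That inference is reasonable but is not an explicit statement.

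Fourth, a simple switch to the last value before onset could do harm. A delayed access-site bleed recognised after haemoglobin had already fallen would be measured from the lowered value. That objection stands against an unrestricted switch, and the fix below is limited accordingly. It also remains true that unscheduled pre-bleed values will differ in age and availability between patients in an open-label trial.

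**Conclusion.** The point holds in a limited form. Note 2 has no end date, and no visible text gives another reference for later bleeds. For a later bleed decided by the haemoglobin drop, the graded drop is off by the change in haemoglobin since TAVR, in either direction. An assumed shift of 1 g/dL is enough to move true drops within 1 g/dL of a threshold on the affected side.

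The effect is confined to descriptive safety tables, mainly after the index hospitalization. A reader might infer that bleeding rates are wrong, that a device difference in late bleeding is diluted, or that the 30-day composite is compromised. None of these is shown: the documents give no haemoglobin course, no bleeding count and no share of events graded on haemoglobin alone, and the same rule applies to both arms. Grades may be wrong for some late events; how many is unknown. No hypothesis test, alpha allocation or sample size is touched.

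This rests on Note 2 being applied as written, on late bleeds being adjudicated as Appendix V events, and on some haemoglobin shift after TAVR.

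**What to change.** Limit Note 2 and name the reference for later events, for example: *For bleeding related to the index procedure, or starting during the index hospitalization, the reference is the pre-operative haemoglobin, even if a lower post-procedure value exists. For later bleeding unrelated to the procedure, the reference is the most recent available haemoglobin before onset; if there is none, the pre-operative value is used. The reference used is recorded.*

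Put the same wording in the CEC charter. Re-check, blinded to arm where feasible, only those later bleeds whose grade was, or could be, decided by the haemoglobin criterion. This includes bleeds already major by another route that might cross ≥5 g/dL.

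The cost is a short change in the appendix and charter, one recorded item, and the re-check of what should be a small number of events. Sites may need to be asked for the pre-bleed value, because Protocol 10.1.5 does not specify it. The drawback is that the reference for late bleeds will vary in age and availability between patients. Recording which value was used lets that be reported by arm.
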